Data for P0 are collected from the time period right before the inspection campaign was announced. All hospitals know that they can be inspected. By collecting data before the campaign was announced we can track changes throughout the inspection cycle and assess to what extent changes are implemented before the inspections are undertaken. P1 is the pre-inspection measurement, and P2 and P3 are post-inspection measurements. The regional inspection teams collect data during the inspection and audits conducted 8 (P2) and 14 months (P3) following the initial inspection. These data serve two purposes. They are used to guide the judgments on whether the inspected hospitals comply with the requirements, and to evaluate how inspections affect the clinical processes involved in diagnosing and treating sepsis.

Figure 2. Illustration of clusters and data collection

We use a two-step approach to identify eligible patients who might have sepsis upon arrival at the hospital. First, a record search of the National Patient Register (NPR) is carried out, using diagnostic codes for infections and sepsis. The NPR is a national common register of all patients and the treatment they have received in Norwegian hospitals. This record search will produce a list of patients with an identification number that will enable the inspection teams to access the corresponding patient records at inspected hospitals. Second, the inspection teams assess the individual patient records for eligibility. The inclusion criteria are clinically suspected infection and at least two systemic inflammatory response syndrome (SIRS) events, excluding elevated leukocytes.⁵³ The inspection teams extract data from the included patient records.

Based on the literature, previous research, and discussion with clinical experts, we identified relevant effect measures that reflect how hospitals handle patients admitted to the hospital with suspected sepsis.^{28 54} These indicators are displayed in box 3. In addition, data are collected for the following control variables: patient sex and age, sepsis with organ dysfunction, and hospital size.

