Descriptive statistics will be used to quantify sample characteristics. All analysis will use patient-level data, collected at four periods for different patients for 24 hospitals – two collections during the control period and two collections during the intervention period for each hospital. In order to compare the various process and outcome measurements (dependent variables) between the intervention and control periods (independent variable), we will use logistic regression models for binary measurements and linear regression models for continuous measurements. The choices of regression methods for the various measurements are outlined in table 3. As recommended in literature, ^{63 64} all models will include time as a covariate to adjust for potential secular changes in the

process and outcome measurements during the study period. The underlying form of time will be included in the models as a linear term, polynomial term, or cubic spline term, as appropriate.

Norway is divided into 18 counties in addition to its capital city, and there are acute hospitals that treat patients with sepsis in all counties. The population density varies between the counties. The smallest acute hospitals serve a population of about 50 000, while the largest serve a population of about 500 000. The sizes of the ICU units and the number of patients with sepsis treated during a year will therefore differ between the included hospitals. This is a national inspection campaign, and hospital in all counties will be inspected. As patients are sampled from different hospitals, a between-hospital variation in measurements is likely, introducing correlated data within the hospitals. To account for this intra-cluster correlation, we will use generalized estimating equations methodology,⁶⁵ specifying an exchangeable working correlation structure, i.e., any two patients are equally correlated within hospitals regardless of time and intervention and control periods. However, as this assumption might not hold for all hospitals, a method for obtaining cluster-robust standard errors of model parameters will be applied.⁶⁶ Finally, as our repeated sampling of patients with sepsis may not be entirely representative of the total population, difference in certain patient characteristics, including age and sex, between comparison periods might arise. In that case, the abovementioned models will also include such covariates for obtaining correct model means.

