The size of the included hospitals differ. The order of the inspections are randomized in clusters of four hospitals, and all the clusters include hospitals with different sizes. To account for intra-cluster correlation, we will use generalized estimating equations methodology,⁶⁵ and we will include hospital size as a covariate in our analytic models. Due to Norwegian topography with long travel distances, patients with suspected sepsis are typically sent to the nearest acute hospital for initial diagnosis and treatment. In some cases patients with septic shock can be transferred to a larger hospital later. We know the number of patients with organ dysfunction admitted to the various hospitals, and can adjust for this in our analysis. We do however not have access to data about comorbidity for the included patients and can therefore not fully adjust for case mix differences between the included hospitals. Our process measures cover the initial steps of the diagnostic and treatment process, which is done in all hospitals irrespectively of size. We compare changes in the effect measures before and after the intervention, and the intervention itself should not affect which patients that are admitted to the different hospitals. Consequently, we have no reason to believe that case mix differences between the inspected hospitals should change before and after the intervention.

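### Age and sex enter the models only if an imbalance is seen, with no trigger defined, so observed balance decides which odds ratio is reported

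*Combined protocol and SAP*

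**What the plan says.** The covariates are described in three places.

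- Data analysis, Statistical analysis: "we will use logistic regression models for binary measurements and linear regression models for continuous measurements", fitted by GEE, and "all models will include time as a covariate". The section then notes that "difference in certain patient characteristics, including age and sex, between comparison periods might arise", and continues: "In that case, the abovementioned models will also include such covariates for obtaining correct model means". The stated purpose is correct means; precision is not mentioned.
- Data collection, Quantitative data: "data are collected for the following control variables: patient sex and age, sepsis with organ dysfunction, and hospital size". This is a statement about collection, not about the model.
- Strengths, potential limitations, and biases: "we will include hospital size as a covariate in our analytic models", which is a commitment. For organ dysfunction the wording is only permissive: "We know the number of patients with organ dysfunction admitted to the various hospitals, and can adjust for this in our analysis".

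Table 3 lists 13 binary measures (logistic) and one continuous measure, length of stay (linear). It names no covariates.

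**The concern.** Different patients are sampled at P0, P1, P2 and P3, so case mix will vary somewhat by chance. All P0 records come from just before 1 October 2015, while later measurements fall in varying calendar months. The plan responds with a look at the data followed by a choice of model, and the choice is not defined. It does not say how a difference is judged, or whether the comparison is control against intervention or among all four time points. It also does not say which characteristics beyond age and sex are in scope. The limitations section says that neither exposure nor data collection can be masked, and no masking of the analyst is described.

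Two things are at stake. The first is an open choice between two results for the same measure. The second is the estimand: in a logistic model the odds ratio conditional on age and sex is not the same quantity as the odds ratio without them, even when both are balanced.

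**Working it through.** There is no stated figure to reproduce, because the point concerns a modelling rule.

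**1. Can the model be written down from the text?** Time is in every model (Statistical analysis). Hospital size is in (limitations section). Age and sex are in only if a difference is seen. Organ dysfunction is possible. Other characteristics are unnamed. No passage overrides the condition on age and sex, so the covariate set is not fixed for any of the 14 measures.

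**2. What does the open choice cost, and what does adjustment gain?**

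Inputs from the protocol: mortality 15% to 11.5%; antibiotics within one hour 50% to 65%; 24 hospitals × 4 time points × 60 = 5760 records for outcomes; alpha 0.05 (two-sided assumed); power 80%.

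Inputs not in the protocol, and therefore assumed: a log odds ratio per SD of age of 0.2, 0.5 or 0.8 for mortality and 0 to 0.5 for antibiotics, and a correlation of 0.1 to 0.3 between age and length of stay.

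Mortality, two groups of 1472 independent patients, with one standardised covariate:

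| Log OR per SD of age | Null error, adjust if imbalance p<0.05 | Null error, better of two results | Log OR, unadjusted → adjusted | SE, unadjusted → adjusted | Power, unadjusted → adjusted |
|---|---|---|---|---|---|
| 0.2 | 5.5% | 5.8% | −0.310 → −0.312 | 0.1098 → 0.1101 | 80.3% → 80.9% |
| 0.5 | 4.7% | 5.6% | −0.312 → −0.321 | 0.1098 → 0.1114 | 80.9% → 82.5% |
| 0.8 | 5.3% | 6.9% | −0.310 → −0.333 | 0.1098 → 0.1140 | 81.2% → 83.8% |

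The null columns use 3000 runs, so the simulation error at 5% is √(0.05 × 0.95 / 3000) = 0.4 points. The fixed rule cannot be distinguished from 5%. Choosing the better result clearly exceeds 5% only at the strongest assumed effect: (6.9 − 5.0)/0.4 ≈ 4.7 simulation errors, against (5.6 − 5.0)/0.4 = 1.5 at the lowest value.

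**3. How far apart are the two odds ratios?** From the same runs, the ratio of adjusted to unadjusted log odds ratio is 0.3119/0.3099 = 1.006, 0.3209/0.3116 = 1.030 and 0.3332/0.3104 = 1.073. At the strongest assumption the reported odds ratio would be exp(−0.3104) = 0.73 or exp(−0.3332) = 0.72, depending on whether the trigger fired.

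**4. Does the result carry over to the clustered model?** The check used exchangeable GEE with robust standard errors, 24 hospitals × 4 × 60, months approximating Table 1, linear time, an assumed hospital SD of 0.4 on the logit scale, and 150 runs per setting.

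- 0.5 per SD: SE 0.1457 → 0.1472 (ratio 1.010); mean |z| 2.06 → 2.07.
- 0.8 per SD: SE 0.1404 → 0.1467 (ratio 1.045); mean |z| 2.14 → 2.17.

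The standard error rises by about 1% to 4.5%. The estimate moves further from zero, so the test gains slightly.

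**5. Other measures.** For antibiotics within one hour (170 independent patients per group), power changes by −0.5 to +1.2 points, which is within simulation error. For length of stay the residual variance factor is 1 − ρ²: 0.99, 0.96 and 0.91 at ρ = 0.1, 0.2 and 0.3, a fall of 1%, 4% and 9%.

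**The case against.** The strongest defence is that the trigger concerns patient characteristics and not results, and that a fixed rule of this kind leaves the error rate close to 5%. Chance imbalance that remains unadjusted is not bias; the unadjusted standard error already allows for it. The limitations section also gives reasons to expect no systematic shift in case mix. All of this stands, and it is why the harm is rated modest. It does not remove the point, because the error-rate result applies to a stated rule and the plan states none.

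A reader might infer that the plan throws away precision. The documents do not support that. They give no prognostic strength for age or sex, and 13 of 14 models are logistic, where adjustment slightly raises the standard error. Multiplying an assumed R² by 5760 (for example 0.020 × 5760 = 115 or 0.076 × 5760 = 438 records saved) applies linear-model reasoning to a clustered binary endpoint. The variance argument fits only length of stay.

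A reader might also infer that each outcome could get its own model. The wording applies the covariates to all the models described before it. Models could diverge only if balance were checked separately in the 33-record process sample and the 60-record outcome sample, and the plan does not say that.

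Nor is fixed adjustment free of consequence. It makes the logistic effect conditional on covariates, while the sample-size targets are marginal percentages.

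**Conclusion.** The point holds as one of pre-specification. Inclusion of age and sex depends on the observed data, the trigger is undefined, the list is open, and three sections of the protocol do not agree on the covariate set. For the 13 logistic measures this leaves the reported odds ratio undetermined until balance has been inspected.

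The size is modest. Error is 5.6% to 6.9% if the better of two results is chosen, against 4.7% to 5.5% under a fixed rule, for one covariate of assumed strength in independent patients. An open covariate list could add to this; that was not quantified. The mortality power gain from fixed adjustment is about 0.5 to 3 points with independent patients and less under GEE. These sizes rest on assumed prognostic strengths. The finding that the rule is undefined rests on the text alone. It is worth fixing because the change is nearly free, not because the results are in serious danger.

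**What to change.** State in the Statistical analysis section that every process and outcome model includes age (continuous, in one form named in advance) and sex as fixed covariates, alongside time and hospital size, whatever balance is observed. Report the estimate without age and sex as a sensitivity analysis.

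Say whether organ dysfunction is also fixed, so that the data collection, analysis and limitations sections agree. This needs a deliberate decision. The key antibiotic measure is described for patients with organ dysfunction, and the covariate drops out of any model restricted to them. The limitations section also expects documentation to improve after inspection, which could affect how organ dysfunction is recorded.

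Because the adjusted odds ratio is conditional on covariates, show standardised (marginal) percentages beside it for comparison with the 15% to 11.5% and 50% to 65% targets.

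The cost is a few sentences and no new data. Table 1 ends in 2018 and the document is dated November 2021. If analyses have already been run, state which models included age and sex and on what ground, and show both versions.
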